4. BACKGROUND AND RATIONALE

Out of a family of six sodium glucose co-transporters, two have been extensively studied for therapeutic indications involving glucose reabsorption from the glomerular filtrate (Hasan, 2014). Sodium glucose co-transporter-1 (SGLT-1), which is mainly found in both the renal tubule and enterocytes lining intestinal villi, transfers glucose across a concentration gradient resulting in glucose absorption from the gut and accounting for 10% of the glucose reabsorption from the renal tubules. Sodium glucose co-transporter-2 (SGLT-2), which is mostly found in the kidneys, is responsible for reabsorbing 90% of the glucose that is filtered by the renal tubules (Tahrani, 2013). Compared with healthy individuals, SGLT-2 is over-expressed and over-activated in those with type 2 diabetes (Rahmoune, 2005).

SGLT-2 inhibitors are a new class of glucose-lowering drugs for the management of type 2 diabetes which reduce plasma glucose levels by increasing urinary glucose excretion (UGE) by up to 60-80g (240-320kCal) per day (Bailey, 2010). SGLT-1 inhibitors and combined SGLT-1 and -2 inhibitors are currently in development.

Several SGLT-2 inhibitors are commercially available and licensed for use in the UK including Dapagliflozin, Canagliflozin and Empagliflozin (Jardiance™). They all lower glycated haemoglobin (HbA1c) effectively compared with placebo (mean difference vs. placebo -0.66% (95% CI, -0.73% to -0.58%) (Vasilakou, 2013). They also result in weight loss of approximately 1.8kg compared with placebo and in combination with other oral hypoglycaemic medications (Vasilakou, 2013). Some of this weight loss can be attributed to fluid loss due to osmotic diuresis from UGE (Bailey, 2011). Weight is lost from both subcutaneous and visceral stores of adipose tissue (Bolinder, 2012).

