Phase II studies have shown that the highly selective and potent SGLT-2 inhibitor Empagliflozin (Jardiance[™]) results in significant reductions in HbA1c level after 12 weeks of therapy compared with placebo (HbA1c 0.4-0.6% reduction with 5-25mg daily dose, p<0.0001) and reduction was similar to that seen with metformin (Ferrannini, 2013). Weight loss of between 1.81-2.33kg was also achieved depending on Empagliflozin (Jardiance[™]) dose along with reduction in fasting plasma glucose (FPG). Similar improvements in HbA1c, weight and FPG have been seen in phase III trials with Empagliflozin (Jardiance[™]) both as monotherapy and in combination with metformin, sulphonylureas or insulin (Roden, 2013; Haring, 2013; Rosenstock, 2014; Ridderstrale, 2014; Kovacs, 2014; Haring, 2014).

Empagliflozin (Jardiance™) is licensed in the UK for use in type 2 diabetes management. In this study, we will be using Empagliflozin (Jardiance™) according to its licensed indications and dosage. The commonest known side-effects include urinary tract and genital mycotic infections which are more frequent in women than men and generally mild in severity. Dehydration and postural hypotension may occur due to volume depletion and modest lowering of blood pressure. Increased urinary frequency may also occur. Increased risk of hypoglycaemia is observed when Empagliflozin (Jardiance™) is combined with sulphonylureas or insulin.

Weight loss from increased UGE and net energy loss with SGLT-2 inhibitors is less than expected as shown by studies in patients with Type 2 Diabetes (T2DM; Ferrannini, 2014). Endogenous glucose production is

markedly increased with shifting of substrate utilisation from carbohydrate to lipid (Ferrannini, 2014; Merovci, 2014).

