Up to 90g of glucose are excreted per day with Empagliflozin (Jardiance™) which equates to 360kCal per day lost by glycosuria. A 90 week study of patients with Type 2 Diabetes treated with Empagliflozin (Jardiance™) 25mg daily showed that average weight loss was 3.2±4.2kg representing a calorie deficit of 51kCal/day (interquartile range [IQR] 112) (Ferrannini, 2015). This was 29%±41% of the expected loss of 11.3±3.1kg predicted by glycosuria of 206kCal per day using a validated mathematical model (http://bwsimulator.niddk.nih.gov). An increase in daily calorie intake of 269kCal/day [IQR 258] and daily energy expenditure appear to be the adaptive responses due to Empagliflozin (Jardiance™) therapy and the combination of SGLT-2 inhibitors and calorie restriction has been recommended by the authors of this study.

Appetite stimulation resulting in increased energy intake may be the underlying mechanism for this weight loss deficit. Furthermore, glucagon response is increased by SGLT-2 inhibition using Empagliflozin (Jardiance™) (Ferrannini, 2014) and dapagliflozin (Merovci, 2014).

Appetite hormones such as peptide Y-Y (PYY) and ghrelin are important in the control of appetite and weight regulation. They are secreted from intestinal L cells which are found in the distal small intestine. Ghrelin, which stimulates hunger, has been shown to increase with weight loss and energy restriction diets (Sumithran, 2011). Glucagon-like peptide 1 (GLP-1) is another hormone which is involved in the regulation of appetite and satiety along with other glucose homeostatic effects (Madsbad, 2014).

There are no studies that have investigated the impact of SGLT-2 inhibitors on appetite hormones and effect on body composition. It is essential to understand these mechanisms in order to maximize the weight loss achievable with these agents. They may need to be combined with appropriate dietary measures such as energy restriction diets and weight-lowering or weight-neutral hypoglycaemic therapies for optimal clinical benefit. The aim of our study is to explore the relationship between appetite hormones and Empagliflozin (Jardiance™) in order to understand the underlying mechanisms for observed weight loss which does not equate with that predicted for these agents.

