5.3 Study End Points

The primary endpoint is effect on appetite hormones (specifically total PYY) with Empagliflozin (Jardiance™) after treatment for 24 weeks.

Secondary endpoints, which are exploratory, are effect on:-

- (i) Appetite hormones ghrelin and GLP-1 and appetite perception
- (ii) Total body weight and change in body composition (fat and fat free mass)
- (iii) Resting energy expenditure
- (iv) Physical activity
- (v) Change in blood and urine biochemical parameters.

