Body composition (fat mass and fat free mass) will be assessed by DEXA scanning at baseline and study end visits using a scanner situated at the Leicester Diabetes Centre according to standard operating procedures.

Biochemical Analysis (visits 1, 2, 3, 4, 5)

Blood tests for FBC, U+E, LFT, lipid profile, HbA1c, FPG, eGFR, glucagon, insulin, leptin, C-peptide, FFA and CRP will be taken (see Abbreviations pg. 11). Urinary glucose excretion (UGE) will be quantified by timed collection to match with appetite hormone sampling. FBC, U+E, lipids, HbA1c, FPG, eGFR and CRP will be

measured once during each visit. Insulin, glucagon, glucose, leptin and C-peptide will be measured at 7 time points specifically at baseline (pre-standardised breakfast), 30 minutes post-breakfast and then 60 minutes, 90 minutes, 120 minutes, 150 minutes and 180 minutes post-breakfast to correspond with the appetite hormones. These blood samples will be analysed at Leicester General Hospital either by the main hospital diagnostic laboratory or by the Research Scientist based at Leicester Diabetes Centre and then disposed of in accordance with the Human Tissue Authority's Code of Practice.

Following analysis, where a participant has consented, samples will be stored indefinitely for future research use.

Energy Expenditure (visits 1, 2, 3, 4, 5)

Indirect calorimetry will be used to assess resting energy expenditure (REE) at baseline, 2, 6, 12 and 24 weeks. This will be measured using a ventilated hood system at the Leicester Diabetes Centre where the participant will place their head under the hood to enable measurement of all expired gases over a predetermined time period according to standard operating procedures.

Physical Activity (visits 0, 3, 4, 5)

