An ActiGraph accelerometer will be provided to the participant to be worn for 8 days (including the clinic day and 7 full consecutive days thereafter) for assessment of step count as a measure of physical activity at visit 0, 6, 12 and 24 weeks. An activPAL inclinometer will also be used to assess posture (i.e., sitting/lying, standing and stepping) for 9 days (including the clinic day and 8 consecutive days thereafter) at visit 0, 12 and 24 weeks. Should study visits occur directly before or during certain holiday periods i.e. Easter, Christmas and New Year, monitors will be sent to participants via the postal system after the holiday period. The study team wish to avoid these holidays periods as it is not habitual behaviour. These will be applied according to Leicester Diabetes Centre standard operating procedures. A log of sleep, wake and monitor removal times will be completed by the participants.

Study Questionnaires (visits 1, 2, 3, 4, 5)

The participant will be asked to complete the following validated questionnaires (see Appendix):-

- > Three-Factor Eating Questionnaire this will assess the participant's current eating habits
- ➤ International Physical Activity Questionnaire (IPAQ) this will assess habitual physical activity in several domains including occupation, leisure, housework
- Visual Analogue Scale (VAS) which will measure perceived hunger, fullness, satisfaction and prospective food consumption ratings

Other Measurements and Data Collection

Anthropometric Measures (visits 0, 1, 2, 3, 4, 5)

Body weight will be measured to the nearest 0.1kg, body fat percentage will be measured to the nearest 1% and muscle mass will be recorded to the nearest 0.1kg using bioelectrical impedance equipment (i.e., Tanita™ scales) while the participant is wearing no shoes and socks and after the removal of any heavy items of clothing.

Height will be measured using a portable stadiometer to the nearest 0.5cm with the participant wearing no shoes.

Waist circumference will be measured to the nearest 0.5cm as the midpoint between the lower costal margin and iliac crest. Hip circumference will be measured to the nearest 0.5cm at the maximum extension of the buttocks ensuring the tape measure is at the same level around the body. Both measures should be taken over underwear or light clothing with the subject standing with their feet together and breathing lightly.

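### Impedance body fat is recorded only to the nearest 1%, which costs a little precision on a listed secondary outcome and could be avoided at almost no cost

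*Protocol*

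**What the plan says.** Protocol 8.5, under anthropometric measures (visits 0 to 5), sets the recording units for the impedance session. For weight, "Body weight will be measured to the nearest 0.1kg". For the other two readings, "body fat percentage will be measured to the nearest 1% and muscle mass will be recorded to the nearest 0.1kg using bioelectrical impedance equipment". The two kilogram readings therefore keep one decimal place and the fat percentage keeps none. No reason is given.

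SAP 5.2(vi) lists body fat (%) among the anthropometric secondary outcomes, with fat mass in kg as a separate item. It does not say which device supplies body fat (%). SAP 5.2 treats values at 2, 6 and 12 weeks as secondary outcomes, and SAP 5.3.3 analyses them with the same baseline-adjusted model as the primary outcome.

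The other body-composition method is DEXA: "Body composition (fat mass and fat free mass) will be assessed by DEXA scanning at baseline and study end visits". Protocol 6.3 and Table 1 confirm that this means visits 1 and 5 only.

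On status, Protocol 5.3 says: "Secondary endpoints, which are exploratory, are effect on" the items that follow, which include body composition.

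**The concern.** Protocol section 4 expects modest weight loss on this drug class: "They also result in weight loss of approximately 1.8kg compared with placebo". For empagliflozin in phase II: "Weight loss of between 1.81-2.33kg was also achieved". Losses of that size move body fat percentage by something like one recording unit (see the working). Recording in whole points therefore looks coarse for this outcome, the more so because weight and muscle mass from the same session are kept to 0.1 kg.

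What is at stake is precision. Each reading, at baseline and at follow-up, carries rounding error that serves no purpose, in a trial planned on 15 completers per arm. The interim visits matter most, because no DEXA value exists there to stand in for the impedance reading.

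**Working it through.** **The plan's own figure.** The documents give no expected change, SD, power or precision for body fat (%). The only planned size is for total PYY AUC: difference 120 pg/ml, SD 96.2 pg/ml, 80% power, two-sided alpha 1.7%. A two-sample t-test calculation gives 14.90, so 15 per arm. Allowing for 20% dropout, 15/0.8 = 18.75, so 19 per arm and 4 × 19 = 76. This agrees with Protocol 11.2. I use 15 per arm below.

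**Step 1: size of the expected change.** Assume 95 kg and 35% fat (neither is in the documents), so fat mass is 33.25 kg. For a weight loss L of which a share f is fat:

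change in body fat % = 100 × (33.25 − fL)/(95 − L) − 35

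| L (kg) | f = 0.5 | f = 1 |
|---|---|---|
| 1.8 | −0.29 | −1.26 |
| 2.33 | −0.38 | −1.63 |

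The recording unit is of the same order as the mean change on drug. These figures are for drug alone; the arms with an energy restriction diet are not estimated.

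**Step 2: variance added by rounding.** Rounding to a unit w adds error variance of w²/12 per reading.

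- w = 1 point: 1/12 = 0.083 per reading; 2 × 1/12 = 0.167 for a change score (error SD 0.41 points).
- w = 0.1 point: 0.01/12 per reading; 0.00167 for a change score.

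**Step 3: effect on the arm comparison.** What matters is this variance against the between-person variance of change. SE of the difference without rounding = SD × √(2/15). Inflation factor = √(1 + 0.167/SD²). Effective n = 15/(1 + 0.167/SD²).

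| Assumed SD of change (points) | SE, unrounded | SE, 1-point rounding | SE increase | Effective n of 15 |
|---|---|---|---|---|
| 1 | 0.365 | 0.394 | 8.0% | 12.9 |
| 1.5 | 0.548 | 0.568 | 3.6% | 14.0 |
| 2 | 0.730 | 0.745 | 2.1% | 14.4 |
| 3 | 1.095 | 1.106 | 0.9% | 14.7 |

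Recording to 0.1 point inflates the SE by less than 0.1% in every row (at SD 1, √(1 + 0.00167) = 1.0008).

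**Step 4: check by simulation.** A baseline-adjusted model was simulated with 15 per arm, baseline SD 7 (assumed) and a true effect of −1 point. The ratios of rounded to unrounded SE were 1.084, 1.034, 1.020 and 1.012 at SDs of 1, 1.5, 2 and 3, in line with the formula. At SD 2 the mean estimate was −1.00 with and without rounding, so there is no bias.

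**Step 5: what this means for power.** At SD 2, power to detect a 1-point difference at alpha 1.7% with 15 per arm is 14.8% with rounding and 15.4% without (normal approximation).

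**The case against.** The strongest objection is that a recording unit close to the mean effect proves little. Rounding errors average out across participants, and the relevant yardstick is the spread of individual changes. On that yardstick the loss is a few per cent of the SE, and at SD 2 the power figures differ by 0.6 percentage points. No conclusion would turn on it. The outcome is exploratory, and weight and DEXA fat mass are untouched. All of this stands, and it is why the point is minor.

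A second objection is that the rounded reading may not feed the week-24 outcome at all. SAP 5.2(vi) names no device for body fat (%), and its list also holds fat mass, bone mass and bone density, which are not among the impedance readings in Protocol 8.5. If body fat (%) at week 24 comes from DEXA, the rounding does not affect that comparison. This also stands, but it leaves weeks 2, 6 and 12, where only impedance is available.

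Two stronger readings are tempting, and the documents support neither.

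- A reader might infer that the device can show body fat to 0.1%, since muscle mass is kept to 0.1 kg. The documents give 0.1 only for the two kilogram readings and say nothing about the display resolution for fat percentage.
- A reader might infer that most participants' recorded changes would collapse to 0 or 1 point. With an assumed mean change of −0.7 and baseline SD 7, simulated recorded changes of 0 or −1 make up 65%, 48% and 38% of participants at SDs of 1, 1.5 and 2. The claim holds only at the smallest of these SDs. The protocol's own 90-week figure for 25 mg, "average weight loss was 3.2±4.2kg", also shows weight change spread widely around its mean.

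**Conclusion.** The point holds as a small, avoidable loss of precision. Whole-point recording adds 0.167 to the variance of a change in body fat %. That raises the SE of the arm difference by about 1% to 4% for SDs of change of 1.5 to 3 points, and by 8% if the SD is as low as 1. It introduces no bias.

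The size rests on SDs that are assumed throughout, on 15 completers per arm, and on rounding errors that behave as uniform and independent, which the simulation supports over this range. If the SD of change is smaller over short intervals, which is also an assumption, the proportional loss would be larger at the early visits.

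The gain from finer recording depends on what the installed device displays, which the documents do not state.

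**What to change.** 1. In Protocol 8.5, replace the 1% recording unit for body fat with the finest resolution the device displays (0.1% where available), and widen the CRF field to match.
2. For visits already completed, re-enter the unrounded value where a device printout or other source record holds it.
3. If the device shows only whole percentages, use body fat % derived from DEXA at visits 1 and 5 for the baseline-to-week-24 comparison. This does not cover weeks 2, 6 and 12, where the whole-point reading would remain.
4. State in SAP 5.2(vi) which device supplies body fat (%) at each visit, so that impedance and DEXA values are not mixed within one change score.

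The cost is a short wording change in each document, one CRF field format, and some data re-entry where source values exist. No procedure or visit is added.

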8.6 Energy Restriction Diet Prescription (Visit 1)

The daily energy restriction diet prescription for each participant will be determined using indirect calorimetry to calculate resting energy expenditure and multiplying by the appropriate activity factor (Mifflin 1990). If for any reason indirect calorimetry cannot be used, energy expenditure will be estimated using the Mifflin-St Jeor equation (MSJE) which uses height, weight and age to calculate resting energy expenditure. The factor will depend on level of activity categorised as sedentary, lightly active, moderately active, very active and extra active. The participant will be advised using standard written dietary information on how to maintain this daily energy restriction throughout the study with regular encouragement from the study team by face-to-face and telephone contact. Target energy intake will be reassessed at visit 3 (6 weeks) and visit 4 (12 weeks).

8.7 Randomisation and Codebreaking

Randomisation will be in a 1:1:1:1 format with stratification by age [1. \leq 50years 2.>50years] and BMI [1. BMI 25.0-29.9kg/m² 2. BMI \geq 30.0kg/m²] at the Baseline visit (Visit 1).

Empagliflozin (Jardiance™) and the placebo will be formulated and supplied in identical tablet form sealed in identical medication packs by Boehringer Ingelheim and supplied to the third-party company ALMAC. ALMAC will then organise blinding, packaging and labelling of both Empagliflozin (Jardiance™) and the placebo. The finished stock will be sent by ALMAC to Leicester General Hospital Pharmacy. The allocation to placebo or Empagliflozin (Jardiance™) will be randomly assigned.

Randomisation will take place at the level of the individual using an independent online computerised randomisation system (Sealed Envelope Ltd.). In the event of an emergency, the investigator will decide on the necessity of unblinding the subject's treatment assignment. The blinded treatment assignments will be accessible to the investigator and Trial Manager should a subject need to be unblinded in an emergency using the Sealed Envelope (Ltd.) system. If unblinding occurs, the investigator must record the reason for unblinding, as well as the date and time of the event. Corresponding information will be recorded on the CRF by the investigator.

8.8 Subsequent Assessments

Table 1 (pg. 27) shows the visit numbers and window periods for the visits. A detailed description of each assessment is provided in Section 8 – Study Procedures (pg. 21).

Visit 0 (Screening Visit) – clinic visit (- 1 week to - 2 days)

During this visit, there will be an eligibility check of inclusion/exclusion criteria, concomitant medications recorded and a safety assessment including physical examination performed. Screening blood tests will be performed if not checked in the last 3 months. Participants will be provided with a diary within which to record their consumption of food and drink throughout the course of the study. Specifically, participants will be asked to record all food and drink consumed, including details about the amount/portion size consumed, a description of what was consumed (i.e., the brand) and the time that it was consumed for a minimum of four days to include the 48 hour restriction period. The diaries will be used to determine whether or not participants have adhered to the 48 hour pre-visit restriction period (see Section 8.4. pg. 22) and their daily energy restriction diet prescription (if applicable; see Section 8.5, pg. 25). The diaries will be checked by a member of the research team at each visit.

Visit 1 (Baseline Visit, 0 weeks) – clinic visit Dispensing Visit

During this visit, there will be a check for ongoing consent to participate in the trial, record of concomitant medications and baseline blood tests performed including renal and liver function tests for safety. Study drugs will be dispensed following randomization. Energy restriction diet will be prescribed if participants are randomized to this intervention.

Visit 2 – clinic visit at 2 weeks (- 5 days to + 5 days)

Dispensing Visit

During this visit, there will be a check for ongoing consent to participate in the trial, record of concomitant medications and blood tests performed for safety including renal and liver function tests. There will be assessment of study drug compliance and/or energy restriction diet compliance. Drug accountability will be performed.

Visit 3 – clinic visit at 6 weeks (- 5 days to + 5 days)

During this visit, there will be a check for ongoing consent to participate in the trial, record of concomitant medications and blood tests performed for safety including renal and liver function tests. There will be assessment of study drug compliance and/or energy restriction diet compliance. Drug accountability will be performed.

Visit 4 – clinic visit at 12 weeks (- 5 days to + 5 days)

Dispensing Visit

During this visit, there will be a check for ongoing consent to participate in the trial, record of concomitant medications and blood tests performed for safety including renal and liver function tests. Study drugs will be dispensed again at this visit. There will be assessment of study drug and/or energy restriction diet compliance. Drug accountability will be performed.

Visit 5 (Final Visit) – clinic visit at 24 weeks (- 5 days to + 5 days)

During this visit, there will be a check for ongoing consent to participate in the trial, record of concomitant medications and blood tests performed for safety including renal and liver function tests. There will be assessment of compliance with study drugs and/or energy restriction diet. Drug accountability will be performed.

Telephone Consultation – 7 days after medication discontinuation (- 3 days to + 3 days)

Participants will be contacted by telephone within 3-7 days after study medication discontinuation in order to capture of any potential Adverse Events.

Table 1 – Measures at each Study Visit

Procedure or assessment during experimental period	Visit 0 (Familiarisation Visit) -1 week to – 2 days	Visit 1 (Baseline) 0 weeks	Visit 2 (2 weeks) - 5 days to + 5 days	Visit 3 (6 weeks) - 5 days to + 5 days	4 th Visit (12 weeks) -5 days to +5 days	5 th and Final Visit (24 weeks) - 5 days to + 5 days	Follow-up Telephone Call (1 week after medication completion) - 3 days to + 3 days
Inclusion/Exclusion criteria Explanation of Study Procedures Informed consent	х						
Confirmation of continued will to participate in the study		Х	Х	Х	Х	Х	
Randomisation		Х					
Demographics	Х						
Smoking status and alcohol intake	х						
Medical history Physical examination	Х					Х	
Concomitant Medication review	х	Х	Х	Х	Х	Х	
Height, weight, waist and hip circumference Resting heart rate and blood pressure	х	Х	Х	Х	х	Х	
Dispensing of Study Drug		Х	Х		х		
Study drug accountability			Х	Х	х	Х	

Physical activity questionnaire (IPAQ)		Х	Х	Х	Х	Х	
Appetite questionnaires (VAS, 3-Factor Eating)		Х	Х	х	Х	Х	
Screening blood test U+E, LFT, lipids, CRP, eGFR, HbA1c	X						
Urine samples		Х	X	х	X	Х	
Biochemical measures FBC,U+E,LFT,lipids,HbA1c,CRP,eGFR, UGE,FPG,FFA (once per visit), insulin, glucose, glucagon, leptin, PYY, ghrelin, GLP-1 (7 times per visit – pre and post meal)		X	X	Х	X	X	
Resting energy expenditure (indirect calorimetry)		Х	X	Х	Х	X	
Physical activity (Accelerometer [A], Inclinometer [I]	X [A,I]			X [A]	X[A,I]	X[A,I]	
Log of wearing monitors		Х	Х	Х	Х	Х	
Body composition (DEXA scan)		Х				Х	

AE reporting		Χ	X	X	X	X	X
Food and Drink Diary	Х	X	X	Х	Х	Х	
Daily Energy Requirement estimation		X					
Standardised Breakfast Meal		V					
calculation	^	^					
Standardised Breakfast Meal		Χ	X	X	X	X	
48hr Pre-visit Standardisation		Χ	X	X	X	X	
24hr Meal Standardisation		Х	X	Х	Х	Х	
Energy Restriction Diet Prescription		Х		Х	Х		
Assessment							
Energy Restriction Diet compliance		Х	X	X	X	X	
check							

